#### 7.7.1 Prohibited and/or Restricted Treatments

Prohibited and/or restricted medications during the study are as described in the study exclusion criteria in Section 6.2. Medications taken within 4 weeks prior to study treatment administration must be recorded on the electronic case report form (eCRF).

Once a participant completes the 26-week main study, modifications to background treatment of lung fibrosis are allowed per clinician discretion or patient preference for those in either cohort during the OTE. As such, during the OTE, anti-fibrotic therapy (eg, pirfenidone or nintedanib) may be started or used in combination, and no restrictions are placed with regards to concomitant use of immunosuppressive medications or corticosteroids. However, all other concomitant medications specified in Section 6.2 #2) will continue to be restricted in the OTE.

No concomitant prescribed medications are to be administered during study unless they are:

- 1) Prescribed for treatment of a clinical condition AND
- 2) Not prohibited in the exclusion criteria or elsewhere in the protocol.

All concomitant therapies (prescription, over the counter, or herbal) must be recorded on the eCRF.

## 7.8 Treatment After the End of the Study

Upon completion of either the main study or the OTE, treatment for IPF or PF-ILD will be at the discretion of the clinical provider.

BMS reserves the right to terminate access to BMS-supplied study treatment if any of the following occur: a) the study is terminated due to safety concerns; b) the development of BMS-986278 is terminated for other reasons, including but not limited to lack of efficacy and/or not meeting the study objectives; c) the participant can obtain medication from a government sponsored or private health program. In all cases BMS will follow local regulations.

#### 8 DISCONTINUATION CRITERIA

## 8.1 Discontinuation from Study Treatment

Participants MUST discontinue the IP for any of the following reasons:

- Participant's request to stop study treatment. Participants who request to discontinue study treatment will remain in the study and must continue to be followed for protocol-specified follow-up procedures. The only exception to this is when a participant specifically withdraws consent for any further contact with him/her or persons previously authorized by participant to provide this information.
- For participants that were unable to receive the evening dose on Day 1 due to having met either asymptomatic or symptomatic low BP criteria and received a reduced dose of BMS-986278 10 mg BID (or placebo for 10 mg BMS-986278 BID) on Day 2, if either asymptomatic or symptomatic low BP criteria are met on Day 2 (refer to Day 1 BP monitoring in Section 5.1.2.1 for details), they will be discontinued from further treatment (but continue in the study). This also applies to the Day 1 and Day 2 visits in the OTE.
- For participants receiving 10 mg BMS-986278 BID (or placebo for 10 mg BMS-986278 BID) after Day 2, if either asymptomatic or symptomatic low BP criteria are met (refer to Day 1 BP monitoring in Section 5.1.2.1 for details), they will be discontinued from further treatment (but continue in the study). This also applies to the OTE.
- For participants receiving 30 mg or 60 mg BMS-986278 (or placebo) after Day 1, if either asymptomatic or symptomatic low BP criteria are met (refer to Day 1 BP monitoring in Section 5.1.2.1 for details), a decision to reduce to 10 mg BMS-986278 BID (or placebo for

10 mg BMS-986278 BID) or discontinue study treatment (but continue in the study) will be discussed with the Medical Monitor/Study Director. This also applies to the OTE.

- Any clinical AE, laboratory abnormality or intercurrent illness which, in the opinion of the investigator, indicates that continued participation in the study is not in the best interest of the participant.
  - This may include progression of the participant's lung fibrosis. Decisions about discontinuing the IP due to progression of disease are left to the discretion of the clinical investigator. Similarly, following discontinuation from study treatment during either the main study or the OTE, decisions regarding potential initiation of antifibrotic or immunosuppressive medications not allowed during the 26-week main study are left to the discretion of the investigator.
- Termination of the study and/or program by BMS.
- Noncompliance of the participant with protocol-mandated procedures based on the judgment and agreement of both the investigator and Sponsor.
- The participant becomes pregnant (study treatment must be discontinued immediately). In the case of pregnancy, refer to Section 9.2.6.
- QTcF > 500 msec and/or changes in QTcF > 60 msec compared to baseline (confirmed on repeat ECG). Sites will inform the medical monitor of ECG values meeting discontinuation criteria.
- For participants with normal Day 1 (Randomization) liver enzymes, total bilirubin, and international normalized ratio (INR), if there is new elevation of ALT or AST > 3× ULN, repeat testing should be performed within 48 to 72 hours. If elevation persists, then standard drug induced liver injury (DILI) discontinuation criteria (see Section 9.2.8) will be applied and study treatment will be discontinued if any of the following occur:
  - ALT or AST  $> 8 \times ULN$
  - ALT or AST  $> 5 \times$  ULN for more than 2 weeks
  - ALT or AST  $> 3 \times$  ULN and (total bilirubin  $> 2 \times$  ULN or INR > 1.5)
  - ALT or AST  $> 3 \times$  ULN with the appearance of fatigue, nausea, vomiting, right upper quadrant pain or tenderness, fever, rash, and/or eosinophilia (> 5%)

Note: If participant lives remotely to study site, a local laboratory may be used for repeat testing, and results should be promptly communicated to the site. Participants meeting the criteria above may have potential DILI (see Section 9.2.8 for additional details).

For participants with elevated AST, ALT, or total bilirubin at Day 1 (Randomization), if there is a new elevation of ALT or AST  $> 2 \times$  baseline, or total bilirubin  $> 1.5 \times$  Day 1 total bilirubin (and to more than ULN), repeat testing should be performed within 48 to 72 hours. If elevation persists, then study treatment will be discontinued if any of the following occur:

- ALT or AST levels increase to  $> 5 \times$  Day 1 (Randomization) measurement.
- ALT or AST levels increase > 2× Day 1 (Randomization) measurements AND the increase is accompanied by a concomitant increase in total bilirubin to > 2× Day 1 bilirubin or the INR concomitantly increases by > 0.3.

- Appearance of fatigue, nausea, vomiting, right upper quadrant pain or tenderness, fever, rash, and/or eosinophilia (> 5%).

Note: If participant lives in a remote location, a local laboratory may be used for repeat testing, and results should be promptly communicated to the site. Participants meeting the criteria above may have potential DILI (see Section 9.2.8 for additional details).

- Loss of ability to freely provide consent through imprisonment or involuntary incarceration for treatment of either a psychiatric or physical illness (eg, infectious disease). (Note: Under specific circumstances and only in countries where local regulations permit, a participant who has been imprisoned may be permitted to continue as a participant. Strict conditions apply, and BMS approval is required.)
- Discretion of investigator.

Refer to the Schedule of Activities (Section 2) for data to be collected at the time of treatment discontinuation and follow-up and for any further evaluations that can be completed.

In the case of pregnancy, the investigator must immediately, within 24 hours of awareness of the pregnancy, notify the Medical Monitor/designee of this event. In most cases, the study treatment will be permanently discontinued in an appropriate manner (eg, dose tapering if necessary for participant safety). Refer to Section 9.2.6.

All participants who discontinue study treatment should comply with protocol-specified follow-up procedures as outlined in the Schedule of Activities (Section 2). The only exception to this requirement is when a participant withdraws consent for all study procedures including posttreatment study follow-up or loses the ability to consent freely (ie, is imprisoned or involuntarily incarcerated for the treatment of either a psychiatric or physical illness).

If study treatment is discontinued prior to the participant's completion of the study, the reason for the discontinuation must be documented in the source documents and entered on the appropriate eCRF page.

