#### 3) Physical and Laboratory Test Findings

- a) Participants with a seated SBP of < 100 mmHg (confirmed by retest within 15 minutes) or seated DBP of < 60 mmHg (confirmed by retest within 15 minutes) at screening or prior to Day 1 study treatment will be excluded from participation in this study.
- b) **Not applicable per Revised Protocol 03.** Participants with orthostatic intolerance, orthostatic hypotension or orthostatic tachycardia (as defined in Section 5.1.2.1) at screening or prior to Day 1 study treatment will be excluded from participation in this study.
- c) Not applicable per Protocol Amendment 04; refer to Exclusion Criterion 3)i. Uncontrolled hypertension, defined as SBP > 160 mmHg or DBP > 100mmHg at screening or prior to the first dose of study treatment. BP may be rechecked no more than twice as clinically indicated.
- d) ALT or aspartate aminotransferase (AST)  $\geq 2^{\times}$  the upper limit of normal (ULN) at screening.
- e) Estimated glomerular filtration rate < 30 mL/min at screening.
- f) Any of the following on ECG prior to study treatment administration, confirmed by repeat:
  - i) Not applicable per Revised Protocol 03.  $PR \ge 210 \text{ msec}$
  - ii) Not applicable per Revised Protocol 03. QRS ≥ 120 msec
  - iii) QT  $\geq$  500 msec
  - iv) QTcF  $\geq$  450 msec
- g) Not applicable per Protocol Amendment 04; refer to Exclusion Criterion 3)j. Baseline total bilirubin >  $1.5 \times$  ULN unless the participant has Gilbert's syndrome. Participants with Gilbert's syndrome must have total bilirubin between  $\ge 1.5 \times$  ULN and  $\le 5 \times$  ULN, with direct bilirubin  $\le$  ULN and no clinical or laboratory evidence of hemolysis.

h) Participants with orthostatic intolerance, orthostatic hypotension (confirmed by retest within 15 minutes) or orthostatic tachycardia (confirmed by retest within 15 minutes) (refer to Section 5.1.2.1 for definitions) at screening or prior to Day 1 study treatment will be excluded from participation in this study.

- i) Uncontrolled hypertension, defined as seated SBP > 180 mmHg or seated DBP > 100 mmHg at screening or prior to the first dose of study treatment. BP may be rechecked no more than twice as clinically indicated.

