- j) Screening total bilirubin  $> 1.5 \times$  ULN unless the participant has Gilbert's syndrome. Participants with Gilbert's syndrome must have total bilirubin between  $\ge 1.5 \times$  ULN and  $\le 5 \times$  ULN, with direct bilirubin  $\le$  ULN and no clinical or laboratory evidence of hemolysis.
- k) Screening WBC  $< 2.5 \times 10^3$ , Hemoglobin < 9 g/dL, platelets  $< 75 \times 10^9$ /L

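### Section 8.1's two liver stopping branches leave out participants whose only Day 1 abnormality is INR, and their ALT/AST limits are inconsistent with each other and with Section 9.2.8

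*Combined protocol and SAP*

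**What the plan says.** Section 8.1 lists liver findings among the reasons for which treatment has to be stopped. It sorts participants by their Day 1 results; the branch numbers used here are labels for convenience.

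- **Branch 1** opens "For participants with normal Day 1 (Randomization) liver enzymes, total bilirubin, and international normalized ratio (INR"). A new ALT or AST above 3 x ULN calls for a repeat test. If it persists, treatment stops at above 8 x ULN; at above 5 x "ULN for more than 2 weeks"; or at above 3 x ULN with bilirubin above 2 x ULN, INR above 1.5, or listed symptoms or eosinophilia. The text refers to Section 9.2.8 for the discontinuation criteria.
- **Branch 2** opens "For participants with elevated AST, ALT, or total bilirubin at Day 1 (Randomization"). A new ALT or AST above 2 x baseline, or a bilirubin rise above 1.5 x Day 1, calls for a repeat test. If it persists, treatment stops when "ALT or AST levels increase to" more than 5 times the "Day 1 (Randomization) measurement"; when ALT or AST is above 2 x Day 1 with bilirubin above 2 x Day 1 or an INR rise above 0.3; or on the listed symptoms or eosinophilia.

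On entry, Section 6.2 criterion 3)d excludes ALT or AST at or above 2 x "the upper limit of normal (ULN) at screening". Criterion 3)j says "Participants with Gilbert's syndrome must have total bilirubin between" 1.5 and 5 x ULN. INR is in the Table 5 laboratory panel; Section 6.2 sets no INR limit and no anticoagulant exclusion.

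**The concern.** A mandatory numeric stop should apply to every randomised participant, and its limits should relate to one another in a way that sites can explain. Here the conditions for the two branches are not complements: Branch 1 requires three things to be normal, while Branch 2 lists abnormalities in only two of them. The limits also use different yardsticks, ULN in one branch and the participant's own Day 1 value in the other, with nothing tying them together.

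At stake is whether a liver-related stop depends on the liver finding or on which analyte happened to be abnormal on Day 1. This is the first study of the drug in patients with pulmonary fibrosis. Section 3.4.4.1 reports no physiologically significant hepatobiliary effects with BMS-986278 to date, but also that a previous LPA1 antagonist was dropped after cholecystitis events. Section 3.4.3.4 notes a slight ALT rise in rats given the drug with pirfenidone, a permitted background therapy.

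**Working it through.** The plan gives no figure to reproduce. The check has three parts: coverage, conversion of the limits to a common scale, and a comparison with Section 9.2.8.

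**1. Coverage.** Each Day 1 analyte is taken as normal or raised.

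| ALT/AST | Bilirubin | INR | Branch 1 | Branch 2 |
|---|---|---|---|---|
| normal | normal | normal | yes | no |
| raised | any | any | no | yes |
| any | raised | any | no | yes |
| normal | normal | raised | no | **no** |

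No profile meets both conditions; one meets neither. If the undefined term for liver enzymes in Branch 1 includes alkaline phosphatase, an isolated rise in that enzyme also falls in neither.

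**2. Limits in multiples of ULN.** Let B be Day 1 ALT (or AST) divided by ULN. Branch 2's ALT/AST-alone stop is above 5B; its ALT repeat-test trigger and bilirubin/INR limb use 2B.

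- Against Branch 1's 8 x ULN stop: 5B > 8 when B > 8/5 = 1.6.
- Against Branch 1's 5 x ULN for more than 2 weeks: 5B > 5 when B > 1.0, that is, for any raised Day 1 value.
- Against Branch 1's 3 x ULN repeat-test trigger: 5B < 3 when B < 3/5 = 0.6.
- Floor of 2B against Branch 1's 3 x ULN: 2B > 3 when B > 3/2 = 1.5.

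| B | 2B | 5B | Branch 1: 3 / 5 for over 2 weeks / 8 |
|---|---|---|---|
| 0.5 (bilirubin-only entry) | 1.0 | 2.5 | ALT-alone stop below the repeat-test trigger |
| 0.8 (bilirubin-only entry) | 1.6 | 4.0 | ALT-alone stop above the repeat-test trigger |
| 1.2 | 2.4 | 6.0 | single-value stop lower than 8; no 2-week limb |
| 1.5 | 3.0 | 7.5 | single-value stop lower than 8; no 2-week limb |
| 1.6 | 3.2 | 8.0 | equal to 8; no 2-week limb |
| 1.9 | 3.8 | 9.5 | higher than 8; no 2-week limb |

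Two examples, both without symptoms or eosinophilia and with stable bilirubin and INR. A confirmed ALT of 9 x ULN stops a Branch 1 participant but not one with B = 1.9, because 9 < 9.5. An ALT held at 7 x ULN stops a Branch 1 participant after 2 weeks; with B = 1.5 it does not trigger the ALT-alone stop, because 7 < 7.5.

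**3. Section 9.2.8.** Branch 1 cites it for discontinuation criteria, but it holds a definition of potential drug-induced liver injury and a duty to report such cases as SAEs, with no stopping rule. For raised baselines that definition requires a baseline multiple and a ULN multiple together: for ALT/AST, above 2 x baseline and above 3 x ULN. Branch 2 uses Day 1 multiples alone for ALT/AST. Its note says participants who meet it may have potential DILI, yet one with B = 0.5 who is stopped at 2.6 x ULN is below the 3 x ULN that Section 9.2.8 requires.

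**The case against.** The strongest reply is that different limits for different baselines are a legitimate design choice and that other safeguards cover the gap. Much of this stands, and it rules out several readings that a reader might infer.

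- **That the branches give one participant contradictory orders.** They do not; no Day 1 profile falls in both. The inconsistency lies between the limits.
- **That a raised baseline always means a looser rule.** At Day 1 values of 1.0 to 1.6 x ULN, Branch 2's single-value stop is 5 to 8 x ULN, equal to or lower than Branch 1's. Below 1.5 x ULN its 2 x Day 1 floor is under 3 x ULN, so stricter. Branch 2 also reacts to an isolated bilirubin rise. Only the missing 2-week limb applies to every raised Day 1 ALT/AST.
- **That participants with Gilbert's syndrome are in general stopped before Branch 1 would retest.** For the ALT-alone limb this needs Day 1 ALT under 0.6 x ULN. It also needs bilirubin still raised on Day 1, since criterion 3)j is a screening limit. Earlier stopping is the cautious direction.
- **That participants with only an abnormal INR are unprotected.** Investigator discretion applies, Section 9.4 requires urgent safety concerns to be discussed with the sponsor at once, Section 9.2.8 reporting covers everyone, and the DMC reviews safety.

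None of these safeguards is an automatic numeric stop, which is what Section 8.1 otherwise provides. The coverage gap and the unexplained crossing of limits therefore remain.

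**Conclusion.** The point holds in four limited parts. (a) A participant whose only Day 1 abnormality is INR has no numeric liver stop. (b) Branch 2's ALT/AST-alone limit exceeds Branch 1's 8 x ULN when Day 1 ALT/AST is above 1.6 x ULN, and for any raised Day 1 ALT/AST there is no counterpart to the 2-week limb. (c) In participants who enter Branch 2 through bilirubin alone, ALT/AST limits are scaled to a normal Day 1 value, so the ALT-alone stop falls below Branch 1's repeat-test trigger when Day 1 ALT is under 0.6 x ULN. (d) The reference to Section 9.2.8 leads to no stopping criteria, and its wording for raised baselines differs from Branch 2.

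The limit approaches 10 x ULN (5 x just under 2) only if the screening cap on ALT/AST also holds on Day 1; a higher Day 1 value would raise it further. How many participants fall in any of these groups cannot be derived from the documents. The primary efficacy model is not in question. This is a gap in a mandatory safety rule, and the documents do not settle which limit is the intended one.

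**What to change.** The sponsor should reconcile the two branches of Section 8.1 with each other and with Section 9.2.8. The revised text should:

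- place every randomised participant, including one whose only abnormality is INR, in exactly one branch, and say which enzymes the Branch 1 condition covers;
- state how Branch 2's Day 1 multiples relate to Branch 1's ULN and duration limbs;
- state how the ALT/AST limits are meant to work when bilirubin alone is raised on Day 1;
- correct the reference to Section 9.2.8 and explain or remove the difference in its wording for raised baselines.

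No threshold or clinical rule is proposed here; those are for the sponsor's hepatic safety group. The cost is a wording amendment and a memo to sites. No new tests are needed, because ALT, AST, bilirubin and INR are already in Table 5. A few participants may be stopped earlier or later than under the present text.

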## 8.1.1 Posttreatment Follow-up

Posttreatment follow-up is of critical importance and is essential to preserving participant safety and the integrity of the study. Participants who discontinue study treatment must continue to be followed according to the protocol.

## 8.2 Discontinuation from the Study

Participants who request to discontinue study treatment will remain in the study and must continue to be followed for protocol-specified follow-up procedures. See the Schedule of Activities (Section 2) for details on the data to be collected at the time of treatment discontinuation and follow-up. The only exception to this is when a participant specifically withdraws consent for any further contact with him/her or persons previously authorized by participant to provide this information.

Protocol Amendment No.: 05

• Participants should notify the investigator of the decision to withdraw consent from future follow-up in writing, whenever possible.

- The withdrawal of consent should be explained in detail in the medical records by the investigator, as to whether the withdrawal is from further treatment with study intervention only or also from study procedures and/or post-treatment study follow-up, and entered on the appropriate eCRF page.
- In the event that vital status (whether the participant is alive or dead) is being measured, publicly available information should be used to determine vital status only as appropriately directed in accordance with local law.
- If the participant withdraws consent for disclosure of future information, the sponsor may retain and continue to use any data collected before such a withdrawal of consent.
- Assessments for the end of treatment/end of study visit must be performed, provided that the participant has not withdrawn consent for these activities.
- All required eCRF pages must be completed, including the date of and explanation for the withdrawal.
- As indicated, appropriate follow-up and/or alternate medical care must be arranged for the participant.

If a participant discontinues prematurely from the intensive PK substudy and/or the PET-Tracer substudy, they may still continue in the main study. If, however, a participant withdraws consent from the main study, they should also discontinue from the substudy.

#### 8.2.1 Individual Discontinuation Criteria

- A participant may withdraw completely from the study at any time at his/her own request, or may be withdrawn at any time at the discretion of the investigator for safety, behavioral, compliance, or administrative reasons. This is expected to be uncommon. Stopping study intervention is not considered withdrawal from the study.
- At the time of discontinuing from the study, if possible, an early termination visit should be conducted, as shown in the Schedule of Activities. See the Schedule of Activities for data to be collected at the time of study discontinuation and follow-up and for any further evaluations that need to be completed.
- The participant will be permanently discontinued both from the study treatment and from the study at that time.
- If the participant withdraws consent for disclosure of future information, the Sponsor may retain and continue to use any data collected before such a withdrawal of consent.

## 8.3 Lost to Follow-Up

- All reasonable efforts must be made to locate participants to determine and report their ongoing status. This includes follow-up with persons authorized by the participant.
- Lost to follow-up is defined by the inability to reach the participant after a minimum of 3 documented phone calls, faxes, or emails as well as lack of response by participant to one registered mail letter. All attempts should be documented in the participant's medical records.

Protocol Amendment No.: 05

Date: 22-Sep-2022 78

• If it is determined that the participant has died, the site will use permissible local methods to obtain date and cause of death.

- If investigator's use of third-party representative to assist in the follow-up portion of the study has been included in the participant's informed consent, then the investigator may use a sponsor retained third-party representative to assist site staff with obtaining participant's contact information or other public vital status data necessary to complete the follow-up portion of the study.
- The site staff and representative will consult publicly available sources, such as public health registries and databases, in order to obtain updated contact information.
- If after all attempts, the participant remains lost to follow-up, then the last known alive date as determined by the investigator should be reported and documented in the participant's medical records.

